#### 4.5.3. Immunogenicity Variables

ADA in K3EDTA plasma will be assessed by using validated bridging electrochemiluminescence assays for Screening, confirmation, and titration. Immunogenicity samples for ADAs will be analyzed by Aptuit (Verona) Srl. Plasma samples for ADA measurements will be collected pre-infusion (60 to 0 minutes prior to start of infusion), Day  $56 \pm 4$ , Day  $112 \pm 7$ , Day  $150 \pm 7$ , and ET (if necessary).

For immunogenicity assays, a positive result will be defined as a positive screening assay followed by a positive confirmatory assay. A negative result will be defined as a negative screening assay or a positive screening assay followed by a negative confirmatory assay. Treatment-induced ADA is defined as a negative result at baseline and a positive result post-dose. Treatment-boosted ADA is defined as a positive result at both baseline and post-dose, with a 4-fold increase to titer. Pre-existing ADA is defined as a positive result at both baseline and post-dose, but without meeting the definition of treatment-boosted ADA.

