## 11. IMMUNOGENICITY

Plasma samples for ADA measurements will be collected pre-infusion (60 to 0 minutes prior to start of infusion), Day  $56 \pm 4$ , Day  $112 \pm 7$ , Day  $150 \pm 7$ , and ET. For immunogenicity assays, baseline will be defined as the pre-infusion ADA measurement collected on Day 1. Unless otherwise specified, the immunogenicity population will be used when summarizing ADA results.

Positive and negative results for immunogenicity assays will be defined as described in [Section 4.5.3](#). ADA titers may be determined in the case of positive ADA results. Positive post-dose ADA results for participants with baseline ADA results will be further defined as treatment-induced ADA, treatment-boosted ADA, or pre-existing ADA, with the definitions of these provided in [Section 4.5.3](#).

The proportion of participants with a positive screening assay will be summarized by dose group and time point in [Table 34](#). The proportion of participants with negative, treatment-induced, treatment-boosted, and pre-existing ADA results will be summarized by dose group and post-dose time point in [Table 35](#). The incidence of ADA, defined as either treatment-induced or treatment-boosted ADA at any time point, will be summarized by dose group in [Table 36](#).

Reverse cumulative distribution (RCD) curves will be presented for post-dose ADA titers by dose group and time point in [Figure 11](#).

If positive ADA results are ascertained and ADA titers are determined, summary statistics of ADA titers including mean titer, SD, median titer, min titer, max titer, geometric mean titer (GMT), geometric mean fold rise (GMFR) from baseline, and percent of participants with at least a 4-fold rise in titer from baseline will be presented by dose group and time point in [Table 37](#). GMT, GMFR, and percent of participants with at least a 4-fold rise in titer from baseline will be presented with corresponding 95% confidence intervals. ADA GMTs will also be presented in [Figure 12](#) by dose group and time point.

Individual ADA assay results will be presented in [Listing 12](#).

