where  $CL$  represents clearance,  $\mu$  is the overall mean of clearance,  $a_{i(k)}$  ( $i = 1, \dots, n_k$ ) is a random participant-specific intercept where there are  $n_k$  participants in the  $k$ th dose group in the pharmacokinetics – immunogenicity subset population with estimable clearance,  $T_{ik}$  represents the value of the ADA titer for the  $i$ th participant in the  $k$ th dose group, and  $\gamma$  represents the change in clearance for a 1-unit increase in ADA titer,  $\beta_k$  ( $k = 1, \dots, 5$ ) represents the fixed effect of dose group on clearance, and the errors  $\epsilon_{ik}$  are assumed independent and identically distributed from the standard normal distribution. Again, dose group ( $\beta_k$ ) will only be included in the model if related to clearance.

For each mixed effects model, either clearance or log-transformed clearance,  $\log(CL)$ , will be used as the response. Whether clearance or log-transformed clearance will be included in the model will be determined after assessing normality and homogeneity of variance using Q-Q plots and plots of residuals against predicted values. The final models used will be stated in the CSR.

For the analysis of the effect of ADA incidence on clearance, the mean clearance will be presented for each ADA result along with the difference in mean clearance between positive and negative ADA, with 95% confidence intervals in **Table 38**. For the analysis of the effect of ADA titers on clearance, the ADA effect parameter estimates,  $\hat{\gamma}$ , will be presented with corresponding standard error and 95% confidence interval in **Table 39**. If the mixed effects models are fit on the log-transformed clearance, statistics and parameter estimates and 95% confidence intervals will be provided after their transformation from the log-transformed analysis back to the original scale for clearance.

The following pseudocode will be used to perform the ANOVA analysis for the effect of ADA incidence on clearance:

```
/* Fit Treatment Group-Specific Mixed-Effects ANOVA model */
proc mixed data=ada_clearance plots=studentpanel(marginal unpack);
class subjid ada(ref='Negative') trtn(ref='1');
model clearance = ada trt/ ddfm=kr2;
random intercept / subject=subjid;
estimate 'ADA Effect' ada 1 -1 / cl alpha=0.05; *use estimate statement to output mean difference;
ods output estimates=estimate_param; *output ADA mean difference estimate and CI;
run;

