**Table 39: ADA Titer – Clearance Analysis Parameter Estimates – Pharmacokinetics – Immunogenicity Subset**

[Implementation Note: If  $\log(CL)$  is used in the ANCOVA model, statistics will be provided after exponentiation to the original units for clearance and the second footnote will be updated to “*Statistics are provided on the original scale for CL, after being obtained using a mixed effects ANCOVA model for  $\log(CL)$ ...*”]

If Dose Group is deemed unrelated to clearance and is excluded from the model, the second footnote will be updated to indicate the model only included centered ADA titer as a covariate.]

Statistic	Result
N	x
ADA Effect, $\hat{\gamma}$	x.xx
Standard Error ( $\hat{\gamma}$ )	x.xx
$\hat{\gamma}$ 95% CI	(x.xx, x.xx)

Notes: N = Number of participants in the Pharmacokinetics – Immunogenicity Subset with estimable clearance (CL). Statistics are obtained using a mixed effects ANCOVA model for CL with a fixed covariate for Dose Group and centered ADA titer as a continuous covariate.  $\hat{\gamma}$  represents the change in clearance for a 1-unit increase to titer from the overall mean titer, holding Dose Group constant.

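### SAP 11.1 models clearance on the untransformed ADA titer, so one outlying titer can largely set the slope and the per-unit estimate can print as no effect

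*SAP*

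**What the plan says.** SAP 11.1 plans two exploratory models when five or more participants have positive ADA results: an ANOVA on ADA incidence and an ANCOVA on ADA titer. In the ANCOVA the regressor "represents the value of the ADA titer for the" participant in question, and the coefficient "represents the change in clearance for a 1-unit increase in ADA titer".

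The Table 39 shell repeats this. The model is fitted "with a fixed covariate for Dose Group and centered ADA titer as a continuous covariate", and the slope "represents the change in clearance for a 1-unit increase to titer from the overall mean titer, holding Dose Group constant". Centering shifts the intercept only; slope, leverage and fitted values stay the same. The ANCOVA pseudocode also enters the ADA variable without transformation.

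A log option exists, but for the response alone: "Whether clearance or log-transformed clearance will be included in the model will be determined after assessing normality and homogeneity of variance". It does not extend to the titer.

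Elsewhere the SAP compares titers with baseline as fold changes. Section 11 lists "geometric mean titer (GMT), geometric mean fold rise (GMFR) from baseline" and the "percent of participants with at least a 4-fold rise in titer from baseline". Section 4.5.3 defines treatment-boosted ADA by a positive result at both times "with a 4-fold increase to titer". Section 11 and Table 37 also tabulate the arithmetic mean titer and SD, so the SAP uses both scales descriptively. Listing 12's example rows show 0 for a negative result and 40 for a positive one.

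**The concern.** Titration results are usually spaced by dilution factors, so their natural increment is a fold step. A straight line in raw titer counts the step from 5,120 to 10,240 as 128 times the step from 40 to 80 (5,120/40), although both are one doubling. Three consequences follow.

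- **Dominance.** A single titer far above the others can decide the slope, and the fit at moderate titers then reflects that one participant.
- **Readability.** A slope per titer unit can be too small to show at the planned reporting precision.
- **Definition.** The model has one titer per participant, while ADA is sampled on Days 56, 112 and 150. The SAP does not say which titer is used, or what value a negative participant takes in the model.

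This is the only planned model relating the size of the ADA response to clearance. A misleading slope or a printed 1.00 would be the study's statement on that question.

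**Working it through.** The documents give no expected titers, dilution factor, power or N for this model, so there is no planned figure to reproduce. The check uses illustrative titers.

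**Inputs from the documents.** At most 30 active participants (five groups of six, SAP Table 1). Five positives, the trigger in SAP 11.1, which leaves 25 negatives. Negatives at 0, as in Listing 12's example. Coefficients reported to 3 significant figures (SAP 13).

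**Assumptions.** The titer sets below; negatives at 20 on the log2 scale, one doubling below the example titer of 40; no dose term unless stated, since SAP 11.1 includes dose only if it is related to clearance.

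**1. Leverage of the top participant.** h = 1/n + (x − x̄)²/Sxx; h = 1 means the fit passes through that point.

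- Positives 40/80/160/320/10,240: x̄ = 10,840/30 = 361.3; Sxx = 104,993,600 − 10,840²/30 = 101,076,747; h = 1/30 + 9,878.7²/101,076,747 = 0.033 + 0.965 = 0.999.
- Positives 40/80/160/320/640: x̄ = 1,240/30 = 41.3; Sxx = 545,600 − 1,240²/30 = 494,347; h = 1/30 + 598.7²/494,347 = 0.033 + 0.725 = 0.76.

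| Positive titers | Raw | log2 |
|---|---|---|
| 40/80/160/320/10,240 | 0.999 | 0.74 |
| 40/80/80/160/1,280 | 0.98 | 0.68 |
| 40/80/160/320/640 | 0.76 | 0.46 |
| 40/80/160/160/320 | 0.64 | 0.41 |
| all equal | 0.20 | 0.20 |

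Average leverage is 2/30 = 0.07. With dose in the model and one positive per dose group, the first set gives 0.999 raw and 0.78 on log2; the ladder to 640 gives 0.79 and 0.55.

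**2. Predictions at moderate titers.** Suppose clearance rises 10% per doubling above 20. Titer 160 is three doublings up: 1.1³ = 1.33, or +33%. Titer 10,240 is nine doublings up: 1.1⁹ = 2.36, or +136%. A raw line from 0 through the top point gives titer 160 a share of 160/10,240 = 1/64, so 136%/64 = 2.1%. With log clearance it gives 2.36^(1/64) = 1.013, or 1.3%.

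**3. Removing one participant.** Noise-free log clearance, dose in the model, truth +20% per doubling. For 40/80/160/320/5,120, dropping the top participant changes the raw slope from 0.000297 to 0.00263, a factor of 8.85. On the ladder to 640 the factor is 1.52.

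**4. Printed result.** With log clearance, a doubling at titer 5,120 is exp(ln 2/5,120) = 1.00014 per unit. At 3 significant figures, or in the two-decimal Table 39 shell, this prints as 1.00. On the log2 scale with negatives at 20, 5,120 is eight doublings up (5,120/20 = 2⁸), so the same effect is 2^(1/8) = 1.09 per doubling.

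**5. Power.** For the 10,240 set, with SD of log clearance 0.25 and a truth of 10% per doubling, simulated power is about 87% raw and 96% on log2; at 5% per doubling, about 37% and 46%. If the truth is instead linear in titer (log-clearance effect 0.86 at 10,240), power is about 90% raw and 78% on log2.

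**6. Value for negatives.** In the first set, moving negatives from 20 to 1 changes the top participant's log2 leverage from 0.74 to 0.49.

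**The case against.** A reader might infer that one participant necessarily fixes the slope and that moderate titers are necessarily predicted to do almost nothing. The documents do not support that. They give no titer distribution or dilution factor, and the 0.999 case rests on an assumed 32-fold gap (10,240/320). On tight ladders the leverage is 0.76 or 0.64, and with equal titers nobody dominates.

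A reader might also infer that the SAP treats titer as multiplicative everywhere except here. It does not: Section 11 and Table 37 tabulate arithmetic mean titer and SD. The narrower statement stands, that the comparisons with baseline are fold changes.

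Two objections to log2 are fair. It leaves the top participant at 0.41 to 0.74 in these sets, because five positives are few on any scale. It also needs a value for negatives, since the log of 0 is undefined, and that value matters. Nor is log2 always more powerful: its advantage assumes a log-linear truth and reverses if the truth is linear in titer.

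The stakes are limited too. The Protocol (10.5.3) leaves the ADA effect on clearance as optional exploration, titers may not be determined at all, and the incidence ANOVA in Table 38 does not depend on titer scale. Individual titers and clearances are listed, so the model can be refitted. None of this removes the untransformed regressor or makes the per-unit slope readable.

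**Conclusion.** The point holds in conditional form and is minor. The regressor is the raw titer, centering does not change that, and the optional log covers clearance only. If one titer is well above the rest, that participant can largely determine the slope, with leverage of 0.98 to 0.999 in the two wide-gap sets against 0.64 to 0.76 on the two tight ladders. The printing problem is separate from dominance: with log clearance, a doubling at titer 5,120 appears as 1.00 per unit however many participants share the high titers. All titer values and the coding of negatives at 20 are assumptions. Power is not a reason for the change, because the comparison depends on the assumed shape of the truth. Safety results and the main PK summaries are unaffected.

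**What to change.** In SAP 11.1, define the covariate as log2 of each participant's highest post-dose titer, with ADA-negative participants set one dilution step below the lowest reportable titer. Report gamma as the change in clearance per doubling of titer, or as a ratio per doubling if log clearance is used. Edit the Table 39 footnote and the ANCOVA pseudocode to match.

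Add two sensitivity analyses: a different value for negatives, and a leave-one-out refit.

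The cost is one derived variable, a footnote, a code edit and two short refits, all of which can be specified before unblinding. The downside is the assumed value for negatives. It needs the assay's lowest reportable titer and dilution step, which the documents do not give, and it affects the result; the first sensitivity analysis is there to show by how much.

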/* If Diagnostics Indicate Log-transformed Clearance is More Appropriate*/
/* Fit Treatment Group-Specific Mixed-Effects ANOVA model for log-transformed clearance */
proc mixed data=ada_clearance plots=studentpanel(marginal unpack);
class subjid ada(ref='Negative') trt(ref='1');
model logclearance = ada trt / ddfm=kr2;
random intercept / subject=subjid;
estimate 'ADA Effect' ada 1 -1 / cl alpha=0.05; *use estimate statement to output log-transformed mean difference;
ods output estimates=estimate_logparam; *output log-transformed mean difference and CI;
run;

/* Transform mean difference estimate and CI limits to original scale (similar for mean clearance) */
```

```
data estimate_logparam; set estimate_logparam;
OG_est=exp(estimate);
OG_lower=exp(lower);
OG_upper=exp(upper);
run;
```

The following pseudocode will be used to perform the ANCOVA analysis for the effect of ADA titer on clearance:

```
/* Fit Treatment Group-Specific Mixed-Effects ANCOVA model */
proc mixed data=ada_clearance plots=studentpanel(marginal unpack);
class subjid trt(ref='1');
model clearance = ada trt/ ddfm=kr2;
random intercept / subject=subjid;
estimate 'ADA Effect' ada 1 -1 / cl alpha=0.05; *use estimate statement to output ADA parameter estimate;
ods output estimates=estimate_param; *output ADA parameter estimate and CI;
run;

/* If Diagnostics Indicate Log-transformed Clearance is More Appropriate*/
/* Fit Treatment Group-Specific Mixed-Effects ANCOVA model for log-transformed clearance */
proc mixed data=ada_clearance plots=studentpanel(marginal unpack);
class subjid trt(ref='1');
model logclearance = ada trt / ddfm=kr2;
random intercept / subject=subjid;
estimate 'ADA Effect' ada 1 -1 / cl alpha=0.05; *use estimate statement to output log-transformed ADA parameter estimate;
ods output estimates=estimate_logparam; *output log-transformed ADA parameter estimate and CI;
run;

/* Transform parameter estimate and CI limits to original scale */
data estimate_logparam; set estimate_logparam;
OG_est=exp(estimate);
OG_lower=exp(lower);
OG_upper=exp(upper);
run;
```

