**Table 38: ADA Incidence – Clearance Analysis Results – Pharmacokinetics – Immunogenicity Subset**

[Implementation Note: If  $\log(CL)$  is used in the ANOVA model, statistics will be provided after exponentiation to the original units for clearance and the third footnote will be updated to “*Statistics are provided on the original scale for CL, after being obtained using a mixed effects ANOVA model for  $\log(CL)$  with fixed covariates for Dose Group and ADA Result, using Negative ADA as the reference group.*”]

If Dose Group is deemed unrelated to clearance and is excluded from the model, the third footnote will be updated to indicate the only fixed covariate in the model was ADA Result.]

Statistic	ADA Incidence Group	
	ADA Positive	ADA Negative
N	x	x
Mean Clearance	x.xx	x.xx
Mean Clearance 95% CI	(x.xx, x.xx)	(x.xx, x.xx)
Difference in Mean Clearance (Positive – Negative)	x.xx	-
Difference in Mean Clearance 95% CI	(x.xx, x.xx)	-

Notes: N = Number of participants in the Pharmacokinetics – Immunogenicity Subset with estimable clearance (CL), excluding those for whom treatment-induced and treatment-boosted ADA cannot be assessed.  
 For this analysis, Positive ADA is defined as experiencing either treatment-induced or treatment-boosted ADA at any time point, and Negative ADA will be defined as not experiencing treatment-induced or treatment-boosted ADA during the study period.  
 Statistics are obtained using a mixed effects ANOVA model for CL with fixed covariates for Dose Group and ADA Result, using Negative ADA as the reference group.

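### If log(CL) is modelled, SAP Tables 38 and 39 print a ratio under labels that describe a difference in clearance, and the ADA-clearance pseudocode does not fit the stated models

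*SAP*

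**What the plan says.** SAP Section 11.1 plans two models if five or more participants have positive ADA results: an ANOVA of clearance on ADA status, and an ANCOVA of clearance on ADA titer. Dose group is kept only if it is found to be related to clearance. The response is CL or log(CL), chosen from residual diagnostics.

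For log(CL), the text says that statistics, estimates and intervals "will be provided after their transformation from the log-transformed analysis back to the original scale for clearance". The code comment is "Transform mean difference estimate and CI limits to original scale (similar for mean clearance)", and the step itself is "OG_est=exp(estimate)", with the same operation on both limits.

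The implementation note of Table 38 says "statistics will be provided after exponentiation to the original units for clearance and the third footnote will be updated to" new wording, which names the log(CL) model but places the statistics on the clearance scale. The rows do not change; one of them is "Difference in Mean Clearance (Positive – Negative)". The note of Table 39 says "statistics will be provided after exponentiation to the original units for clearance and the second footnote will be updated to" similar wording. Its existing footnote says that the slope "represents the change in clearance for a 1-unit increase to titer from the overall mean titer, holding Dose Group constant".

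The CLASS statement of the untransformed ANOVA reads "class subjid ada(ref='Negative') trtn(ref='1')", while its MODEL statement uses `trt`.

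**The concern.** Exponentiating a difference of log means gives a ratio of geometric means. It is not on the clearance scale and has no clearance units. Yet Section 11.1, the code comment and the Table 38 note all say that it is, and neither the section nor the shells call it a ratio. The SAP draws these distinctions elsewhere: Section 11 reports a geometric mean fold rise for titers, and Table 29 gives the mean and the geometric mean of CL in separate rows.

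If the SAP is followed exactly, a finding of no ADA effect appears as a difference of 1.00 with an interval that excludes 0. Immunogenicity and PK are the secondary objectives of this first-in-human trial, and those planning later studies may read that row as an ADA effect on clearance. In Table 39, a shallow slope per titer unit prints as 1.00 and does not show the effect.

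The code faults matter because Section 11.1 commits to using this code for the analyses.

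**Working it through.** The SAP gives no numerical result for this analysis, so there is none to reproduce.

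**Inputs from the documents.** There are 30 active participants, 6 in each of 5 dose groups (SAP Table 1). The trigger is five positives (SAP 11.1). Non-human primate clearance is 0.002 L/day/kg (Protocol 2.1). The example titers are 0 and 40 (SAP Listing 12, a mock-up and not data).

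**Assumptions.** Log-scale SD is 0.2, 0.3 or 0.4. All 30 participants are evaluable and exactly 5 are ADA-positive. `trt` is coded 1 to 5. Human CL is 0.5 to 2 times the primate value. Intervals use ordinary residual degrees of freedom.

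**What is printed.** Let d = mean log CL (positive) − mean log CL (negative). Then exp(d) = GM(positive)/GM(negative). If there is no effect, d = 0 and exp(d) = 1. Because exp() is always positive, the interval cannot contain 0.

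**Standard-error factor of the ADA contrast** (square root of its diagonal element of the inverse of X'X):

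- One positive per dose group, five dose levels: √(1/(5 × 5/6)) = √0.24 = 0.490. A numeric trend or no dose term gives the same value.
- All five in one dose group, five levels: √(1/5 + 1/1) = 1.095.
- All five in the lowest dose group, numeric trend: √(1/(25/6 − 100/60)) = √(1/2.5) = 0.633.

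**95% CI when the observed ratio is exactly 1** = exp(± t × SD × factor):

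| Case | SD 0.2 | SD 0.3 | SD 0.4 |
|---|---|---|---|
| Dose retained (df 30 − 6 = 24), one positive per group | 0.82–1.22 | 0.74–1.35 | 0.67–1.50 |
| Dose retained (df 24), all five in one group | 0.64–1.57 | 0.51–1.97 | 0.40–2.47 |
| Dose dropped (df 30 − 2 = 28), any split | 0.82–1.22 | 0.74–1.35 | 0.67–1.49 |

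In every case the difference row reads 1.00, while the actual difference is 0. Simulation under no effect (2,000 runs for each combination of 5 or 10 positives and the three SDs, dose retained) agrees. The exponentiated interval excluded 1 in 4.2% to 6.6% of runs, close to the nominal 5%, and excluded 0 in 100%.

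**Size on the clearance scale.** 0.002/24 = 8.3e-5 L/h/kg. A ratio of 1.25 prints as 1.25, but the real difference is 0.25 × 8.3e-5 = 2.1e-5 L/h/kg (1.0e-5 to 4.2e-5 over the assumed range of human CL).

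**Table 39.** exp(γ) is a factor per titer unit. It prints as 1.00 at two decimals if it is at least 1 but below 1.005. Over 40 units, 1.005^40 = 1.22, so any total rise below 22% prints as 1.00. A doubling over 40 units is 2^(1/40) = 1.0175, printed as 1.02. A doubling prints as 1.00 only if spread over more than ln 2/ln 1.005 ≈ 139 units. The scale of the Standard Error row is undefined: the note exponentiates the statistics without exception, but the code transforms only the estimate and limits.

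**Dose term in the untransformed ANOVA.** `trtn` is classified but `trt` is modelled. If `trt` is numeric and dose is retained, it enters as a one-df trend (residual df 30 − 3 = 27) instead of the stated five-level effect (df 24). The log(CL) ANOVA uses `trt` in both statements. The residual plots used to choose the response scale would then come from models with different dose terms, and with all five positives in the lowest dose group the SE factor would be 0.633 instead of 1.095.

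**ANCOVA code.** The stated covariate is titer. Both blocks model `ada`, which is not in CLASS, and apply the two coefficients 1 and −1 to a term with a single slope. No titer variable appears, whichever response scale is used.

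**The case against.** The strongest objection is that the error would be seen. Table 38 prints each group's clearance above the difference row. With means near 8e-5 L/h/kg, a difference of 1.00 is about 12,000 times either mean. The revised footnote must name the log(CL) model, and Section 11.1 promises to state the final models in the study report. That lowers the chance of a misreading. It does not make the label correct, and the same footnote tells the reader that the value is on the clearance scale.

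The analysis may also never run. Protocol 2.1 expects low immunogenicity, and Protocol 2.3.1 reports no ADA in treated animals. That limits the priority, not the fault.

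Three narrower points stand:

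- The documents do not give the type of `trt`. If it is character, the block should fail instead of fitting a trend. The code still departs from the stated model, although the text makes the intended model clear.
- The replacement footnote of Table 39 ends in an ellipsis. That the change-in-clearance sentence survives is the natural reading, but it is not stated.
- The trigger counts positive ADA results, while the model counts only treatment-induced or treatment-boosted ADA. Five positives in the model is therefore an assumption.

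Finally, a difference of back-transformed means with a suitable interval would also match the present row label. That is a legitimate alternative, but the SAP's code does not compute it. A ratio keeps the SAP's own method.

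**Conclusion.** The concern holds. If log(CL) is chosen, following the SAP to the letter prints a ratio with null value 1 under a label that implies a difference with null value 0. Table 39 has the same fault for the titer slope. This is algebra and depends on none of the assumed values; those only illustrate its size.

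The code faults are also present as written. The consequence of the `trtn`/`trt` mismatch depends on `trt` being numeric and dose being retained. The ANCOVA fault applies on either response scale.

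The scope is limited. Protocol 10.5.3 makes the analysis optional and exploratory. It needs at least five ADA positives, the labelling faults need log(CL), and Table 39 also needs titers to have been determined. No primary or safety result changes. The correction should be made before the analysis is run.

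**What to change.** For the log(CL) case:

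- **Table 38:** relabel the rows as geometric mean clearance (95% CI) and geometric mean ratio, positive/negative (95% CI, null 1). Correct the wording about original scale or units in Section 11.1, the code comment and the table note.
- **Table 39:** report exp(γ) as a ratio with its CI over a pre-specified titer increment large enough to show at the printed precision. Give the standard error on the log scale only, or omit it.

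Keep the present labels for untransformed CL.

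In the code, use the same dose variable in CLASS and MODEL in the ANOVA. In the ANCOVA, use a named continuous titer variable with a single-coefficient ESTIMATE statement.

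Optional tidying that leaves the ADA estimate unchanged:

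- Drop the random intercept, which cannot be separated from the residual with one CL per participant.
- State the errors as N(0, σ²), because the text fixes the variance at 1 while the code estimates it.
- Make the text, code and Table 39 agree on whether titer is centred.

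The cost is an edit to Section 11.1, its pseudocode and two table shells. There is no data or operational cost, and no change to the five-positive trigger or to the diagnostic choice between CL and log(CL).
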